4.4.2.3 Keyhole Limpet Hemocyanin

Levels of anti-KLH antibody IgG in patients in Groups A and B measured at 4, 8, and 12 weeks after first KLH administration will be summarized descriptively by treatment group using the same summary statistics as presented in Section 4.4.1 for the primary immunology endpoint.

Levels of anti-KLH antibody IgM in patients in Groups A and B measured over time at 4, 8, and 12 weeks after first KLH administration will be summarized descriptively by treatment group using the same summary statistics as presented in Section 4.4.1 for the primary immunology endpoint.

4.4.2.4 Influenza Vaccine Response

Between-group comparisons of influenza vaccine response require comparison of Groups A2 and B. As noted above in Section 4.4.2.2, comparisons between Groups A2 and B should be interpreted with some caution, since patients were not assigned to Group A2 randomly (patients were randomized to Group A or B, and within Group A were non-randomly assigned to Group A1 or A2, based on seasonality considerations).

The number and percentage of patients in Groups A2 and B who achieve seroprotection, defined as specific HI titers >40 at 4 weeks after vaccination, will be presented by treatment group. The difference between Groups A2 and B in seroprotection rates, and the associated 95% CI will also be presented using a normal approximation method.

The number and percentage of patients in Groups A2 and B who achieve a 2-fold increase in specific HI titers at 4 weeks after vaccination will be presented by treatment group. The difference between Groups A2 and B in the proportion of patients achieving a 2-fold increase, and the associated 95% CI will also be presented using a normal approximation method.

The number and percentage of patients in Groups A2 and B who achieve a 4-fold increase in specific HI titers at 4 weeks after vaccination will be presented by treatment group. The difference between Groups A2 and B in the proportion of patients achieving a 4-fold increase, and the associated 95% CI will also be presented using a normal approximation method.

The number and percentage of patients in Groups A2 and B who achieve seroconversion at 4 weeks after vaccination, defined as a pre-vaccination antibody titer <10 and a HI titer >40 at 4 weeks after vaccination, will be presented by treatment group. The difference between Groups A2 and B in seroconversion rates, and the associated 95% CI will also be presented using a normal approximation method.

Strain-specific GMTs in patients in Groups A2 and B measured 4 weeks after vaccination will be summarized descriptively by treatment group using the same summary statistics as presented in Section 4.4.1 for the primary immunology endpoint.

Strain-specific GMT ratio (post-vaccination:pre-vaccination) in patients in Groups A2 and B will be summarized descriptively by treatment group; summary statistics calculated will include mean, median, SD, minimum, and maximum.

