 - Proportion of patients who achieve seroprotection defined as specific HI titers >40 at 4 weeks post-immunization
 - Proportion of patients who achieve a 2-fold increase in specific HI titers at 4 weeks post-immunization
 - Proportion of patients who achieve a 4-fold increase in specific HI titers at 4 weeks post-immunization
 - Proportion of patients with seroconversion (i.e., a pre-vaccination antibody titer < 10 and a post-vaccination HI titer >40);
 - Strain-specific geometric mean titers (GMTs) at baseline and at 4 weeks post-vaccination
 - Strain-specific GMT ratio (post-vaccination:pre-vaccination)
- MRI assessments to evaluate the long-term effects of OCR on MRI parameters of disease activity during the OOE Period.

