4.1.2 Observed Cases Population

The Observed Cases (OC) Population is defined as all randomized patients who complete the ISP. Patients who receive an incorrect medication or vaccination rather than the one that they are assigned to will be summarized according to their randomized treatment group.

All immunization outcome measures will be analyzed using the OC Population.

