4.4 OUTCOME ANALYSIS

No hypothesis testing will be performed.

For immunology endpoints, pre-immunization levels are those obtained immediately prior to administration of a vaccine.

Patients with missing immunology assessment data will not be included in the calculations. No missing data imputation methods will be applied.

For immunology endpoints, except where stated, tabular presentations will show Group A (Groups A1 and A2 combined) and Group B.

Summaries will be presented for the OC Population only.

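### Influenza seroconversion is open only to patients starting below a titer of 10 but is reported over all A2 and B patients; show the count starting below 10 and the rate among them beside the planned rate

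*SAP*

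**What the plan says.** Protocol 3.4.2 lists, among the influenza outcome measures, "Proportion of patients with seroconversion (i.e., a pre-vaccination antibody titer < 10 and a post-vaccination HI titer >40". SAP 4.4.2.4 uses the same definition, "defined as a pre-vaccination antibody titer <10 and a HI titer >40 at 4 weeks after vaccination". Neither has a rule for a patient whose pre-vaccination titer is 10 or higher. The tetanus definition in SAP 4.4.1, by contrast, has one criterion for low and another for higher starting titers.

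On the denominator, SAP 4.4.2.4 promises "The number and percentage of patients in Groups A2 and B who achieve seroconversion at 4 weeks after vaccination", without limiting it to patients who start below 10. Two other provisions decide who is left out. SAP 4.1.2 states "All immunization outcome measures will be analyzed using the OC Population", which means patients who complete the Immunization Study Period. SAP 4.4 adds "Patients with missing immunology assessment data will not be included in the calculations". Starting titer is not a ground for exclusion.

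The comparison is unadjusted: "The difference between Groups A2 and B in seroconversion rates, and the associated 95% CI will also be presented using a normal approximation method". The same section warns that A2-B comparisons need some caution because "patients were not assigned to Group A2 randomly".

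**The concern.** A percentage built this way has two components: how many patients were able to seroconvert at all, and how many of those did. If the first component differs between A2 and B, the reported difference moves even when vaccine response among initially seronegative patients is the same. A real difference in response can likewise be diluted or cancelled.

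The design gives reasons to expect that the first component may differ:

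- Randomization was to A or B only. Under protocol 3.1, A2 is filled preferentially in the first influenza season and the remaining Group A patients go to A1. No matching rule is stated for B, and the exclusion criteria (protocol 4.1.2) foresee two seasons' vaccines.
- Protocol 4.4.2.5 places the A2 vaccination at Weeks 12 to 20, after ocrelizumab. Group B is vaccinated at Weeks 1 to 12, or later with the ocrelizumab infusion delayed, so its pre-vaccination titer is taken without ocrelizumab.

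No hypothesis test is planned, so the estimate and its interval are the whole result for this endpoint. A reader should be able to tell a weaker response from a smaller number of seronegative patients.

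**Working it through.** The documents give no rate, precision or sample size for influenza seroconversion, so there is no planned figure to reproduce.

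**Inputs from the documents.** Group A2 has about 33 patients, minimum 30 (protocol 3.1). Group B has about 33, being one third of about 100 under 2:1 randomization. The interval is a normal-approximation 95% CI (SAP 4.4.2.4).

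**Inputs assumed.** The share *s* with pre-vaccination titer <10, and the probability *c* that such a patient reaches >40 at 4 weeks. The documents give neither, so ranges are shown.

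**Step 1: what the planned rate measures.** Since seroconversion requires a start below 10, the rate in a group is *s* × *c*. The reported difference is

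D = sA·cA − sB·cB = (sA − sB)·(cA + cB)/2 + (cA − cB)·(sA + sB)/2.

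The first term is starting serostatus; the second is response. The first vanishes only if the shares are equal (or if nobody responds). With equal shares, D equals *s* times the difference in response.

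**Step 2: equal response, unequal shares (33 per group).** Half-width = 1.96 × √[pA(1 − pA)/33 + pB(1 − pB)/33].

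| c, both groups | sA | sB | Rates A2 / B | D | 95% CI |
|---|---|---|---|---|---|
| 0.6 | 0.5 | 0.3 | 30% / 18% | +12 points | −8 to +32 |
| 0.8 | 0.5 | 0.3 | 40% / 24% | +16 points | −6 to +38 |
| 0.8 | 0.6 | 0.3 | 48% / 24% | +24 points | +2 to +46 |

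Swapping the shares reverses the sign. Over c = 0.4 to 0.8 and sA = 0.4 to 0.6 against sB = 0.3, the spurious difference runs from 4 to 24 points. Of the nine scenarios computed on that grid, only the last row of the table gives an interval that excludes zero. With 30 patients in A2 the point values are unchanged and the intervals are slightly wider.

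**Step 3: response halved in A2 (cA = 0.4, cB = 0.8).**

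- sA = sB = 0.3: 0.12 − 0.24 = −12 points (95% CI −30 to +6).
- sA = 0.6, sB = 0.3: 0.24 − 0.24 = 0 points; the effect is fully masked.
- sA = 0.3, sB = 0.5: 0.12 − 0.40 = −28 points (95% CI −48 to −8).

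**Step 4: precision if restricted to patients starting below 10.** With c = 0.6 in both groups, half-width = 1.96 × √(2 × 0.24/n), n = 33·s.

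| s | n per group | Half-width |
|---|---|---|
| 0.3 | about 10 | 0.43 |
| 0.4 | about 13 | 0.37 |
| 0.5 | about 17 | 0.33 |
| 0.6 | about 20 | 0.31 |

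The all-patient difference at s = 0.3 and c = 0.6 has a half-width of 0.185.

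**The case against.** The best defence is that going from below 10 to above 40 is a coherent joint event, defined identically in protocol and SAP, and that other planned output already covers the problem. Any such rise is more than 4-fold, so every seroconverter is also a 4-fold responder, and SAP 4.4.2.4 reports the 4-fold difference with its CI for patients at any starting titer. It also reports the 2-fold rate, seroprotection, GMTs and post:pre ratios. SAP 4.3.7 tabulates pre-vaccination titers for A2 and B, so a large imbalance would show. The SAP already urges caution on A2 versus B. The endpoint is secondary, and no error rate or sample size depends on it.

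Most of this stands, and it limits the weight of the point. It does not remove it. The companion endpoints do not change what the seroconversion estimate measures. The caution is general and is not tied to the denominator. SAP 4.3.7 counts values at or below the limit of quantification, not below 10, and the limit for the HI assay is not stated, so the share starting below 10 may not be readable from that table.

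A second objection concerns the remedy. Restricting to titers below 10 conditions on a measurement generally taken after ocrelizumab in A2 but without it in B. If ocrelizumab or season shifts starting titers, the two seronegative subsets are different kinds of patients. (SAP 4.3.7 says the influenza pre-vaccination sample may fall before or after the start of ocrelizumab; the A2 schedule in protocol 4.4.2.5 places it after.) This objection also stands. A reader might infer that the restricted rate should replace the planned one as the unbiased comparison. The documents do not support that: A2 was not randomly formed, and restriction does not repair it.

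**Conclusion.** The point holds as one of interpretation and reporting. On the plain reading of SAP 4.4.2.4 with 4.1.2 and 4.4, the A2-B seroconversion difference mixes the share starting below 10 with the response among those patients, in a comparison that randomization does not protect. The SAP does not spell out the denominator, so this rests on its ordinary wording.

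Size and direction are unknown. The 12 to 16 points are an illustration on assumed shares of 50% and 30% and an assumed common response of 60 to 80%; with equal shares there is no spurious difference. A reader might infer that the planned interval is likely to show a false effect. The documents do not support that: at about 33 per group both illustrative intervals include zero, and excluding zero with equal response took a 60% versus 30% split with 80% response. Nor is the definition an error or a contradiction. The primary tetanus result is not affected. This is a cheap improvement to one secondary, descriptive endpoint.

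**What to change.** Keep the planned all-patient seroconversion rate and difference in SAP 4.4.2.4. Beside it, for each strain, add as a supportive analysis:

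- the number and percentage in A2 and in B with a pre-vaccination HI titer <10;
- the number and percentage of those patients who reach >40 at 4 weeks;
- the A2-B difference in that restricted rate, with its 95% CI.

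State the denominator of the planned rate explicitly. Add a note that the restricted comparison is imprecise and still non-randomized, because it selects on a titer generally measured after ocrelizumab in A2 but without it in B. Direct the reader to the 4-fold-rise endpoint, which includes patients at any starting titer.

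The data are already collected, so the cost is a few lines of SAP text, one filter and extra rows per strain. The price in precision falls only on the supportive figures: half-widths of about 0.31 to 0.43 if 60% down to 30% of 33 patients per group start below 10 and 60% of them respond.

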Patients in Group A are to first receive OCR (Day 1/Week 1 [Dose 1 Infusion 1] and Day 15/Week 2 [Dose 1 Infusion 2]), and 12 weeks post-OCR treatment, are to receive a similar immunization course to Group B. Group A will be further subdivided into two groups to evaluate the effectiveness of a booster 13-PCV vaccination or of influenza vaccination.

For the primary objective and for secondary objectives 1 and 3, Group A (active) will be compared with Group B (control).

To determine the outcomes of secondary objectives 2 and 4, patients in Group A will be split into two groups with 50% of patients in each group (Groups A1 and A2). Patients will be assigned to either Group A1 or A2:

- Group A1 will receive booster 13-PCV (approximately 33 patients)
- Group A2 will receive the influenza vaccine (approximately 33 patients but a minimum of 30 patients).

A minimum of 30 patients will be assigned to Group A2 during the first influenza season. If a minimum of 30 patients (a maximum of 33) are assigned to Group A2 and receive the first year's influenza vaccine, all remaining patients in Group A will be assigned to Group A1 and receive the 13-PCV booster. If less than 30 patients have been assigned to Group A2 during the first influenza season, further patients assigned to Group A2 will have influenza vaccine visits during the subsequent influenza season (i.e., when the next year's vaccine becomes available).

The primary and secondary humoral immunity and immunophenotyping outcomes are to be measured by flow cytometry and quantitative Ig measurements.

Approximately 30–35 centers will participate in the study in the United States/North America. This study consists of up to five study periods:

- Screening Period
- Immunization Study Period

Group A: Immunization Study Period and OCR treatment starts at Day 1/Week 1.

Patients will receive 300 mg of open-label OCR on Day/Week 1 (Dose 1 Infusion 1) and Day 15/Week 2 (Dose 1 Infusion 2). Patients in Group A will be split and be assigned to either Group A1 (booster 13-PCV) or Group A2 (influenza vaccine). At Day 85/Week 12 patients will start to receive immunizations and undergo post-immunization assessments. For all patients in Group A, the Immunization Study Period will end on Day 169/Week 24.

Group B: Patients will not receive OCR. At Day 1/Week 1, patients will start to receive immunizations and undergo post-immunization assessments. For Group B, the Immunization Study Period will end at Day 84/Week 12.

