2.2 SECONDARY OBJECTIVES

The secondary objectives of this study are:

1. To characterize the humoral immune response (IgG) to the 23-PPV in Group A (Groups A1 and A2) patients compared with Group B patients.
2. To characterize the humoral immune response (IgG) in OCR-treated patients to 23-PPV boosted by a subsequent 13-PCV booster (Group A1) compared with unboosted 23-PPV (Group A2).
3. To characterize the humoral immune response (IgG and IgM) to KLH in Group A patients compared with Group B patients.
4. To characterize the humoral immune response (HI titers) to influenza vaccine in OCR-treated patients (Group A2) patients compared with patients not treated with OCR (Group B).

5. To evaluate the long-term effects of OCR on MRI parameters of disease activity during the Optional Ocrelizumab Extension (OOE) Period of the study.

Group A will be split into Group A1 (patients will receive the booster 13-PCV), and Group A2 (patients will receive the influenza vaccine; see Section [3.1](#)).

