3.4.2 Secondary Outcome Measures

The secondary outcome measures are as follows:

- TT response:
 - The proportion of patients in Groups A (A1 and A2) and B with a positive response (IgG) to TT vaccine measured 4 weeks after TT vaccine administration.
 - The proportion of patients in Groups A (A1 and A2) and B with a 2-fold increase in tetanus antibody titers, or with tetanus antibody titers ≥ 0.2 IU/mL, measured 4 weeks after the immunization of patients with pre-immunization tetanus antibody titers ≥ 0.1 IU/mL or with pre-immunization tetanus antibody titers < 0.1 IU/mL, respectively.
 - Mean levels of anti-tetanus antibody in patients in Groups A (A1 and A2) and B measured immediately prior to and 4 weeks after a booster TT vaccine.
- Pneumococcal vaccine response:
 - The proportion of patients in Groups A (A1 and A2) and B with positive antibody responses against an individual pneumococcal serotype measured 4 weeks after the 23-PPV (23 serotypes). (A positive response against a serotype is defined as developing a 2-fold increase in antibody level or a > 1 μ g/mL rise in level compared with pre-immunization levels. Pre-immunization levels are those obtained immediately prior to receipt of 23-PPV.) Post-immunization levels will be measured 4 and 8 weeks after 23-PPV administration for Groups A1, A2, and B.
 - The proportion of patients in Groups A (A1 and A2) and B with a positive response against at least 2 out of 23 pneumococcal antibody serotypes measured 4 weeks after administration of 23-PPV vaccine.
 - The proportion of patients in Groups A (A1 and A2) and B with positive responses against at least 50% of the serotypes (≥ 12 of 23) measured 4 weeks after administration of 23-PPV vaccine.
 - Mean levels of anti-pneumococcal serotype-specific antibody in patients in Groups A (A1 and A2) and B measured immediately prior to and 4 and 8 weeks (which is 4 weeks after Group A1 patients received the 13-PCV booster) after administration of 23-PPV vaccine.
- KLH response:
 - Mean levels of anti-KLH antibody (IgG and IgM) in patients in Groups A (A1 and A2) and B measured immediately prior to the first administration of KLH and 4 weeks after the last administration of KLH.
 - Mean levels of anti KLH antibodies (IgG and IgM) in patients in Groups A (A1 and A2) and B measured over time at 4, 8, and 12 weeks after first KLH administration.

- Strain-specific influenza vaccine response in Groups A2 and B:

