6.4 IMMUNOLOGY ENDPOINTS

6.4.1 Analysis of Immunology Endpoints

Primary Endpoint

The proportion of patients with positive responses to TT vaccine measured 8 weeks after administration of the TT vaccine for Group A and Group B will be assessed.

For patients with pre-immunization tetanus antibody titers <0.1 IU/mL, a positive response to the booster immunization is defined as an antibody titer ≥ 0.2 IU/mL measured 8 weeks after the immunization. For patients with pre-immunization tetanus antibody titers ≥ 0.1 IU/mL, positive response to the booster immunization is defined as a 4-fold increase in antibody titer measured 8 weeks after the immunization. Pre-vaccination levels are those obtained immediately prior to receipt of a vaccine.

Secondary Endpoints

All secondary endpoints are as defined in Section 3.4.2. Descriptive statistical analyses will be used to compare the proportion of patients with responses in the assessments and groups as specified in that section. The mean level of antibody parameters will be presented using geometric means.

Exploratory analyses will be performed to assess the possible relationship among measurements, and clinical response and will be specified in the statistical analysis plan.

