2.2.2 Secondary Outcome Measures

The secondary outcome measures are as follows:

- TT response

The proportion of patients in Groups A (A1 and A2 combined) and B with a positive response (IgG) to TT vaccine measured 4 weeks after booster TT vaccine administration (defined fully in Section [4.4.2.1](#))

Mean levels of anti-tetanus antibody in patients in Groups A (A1 and A2 combined) and B measured immediately prior to and 4 weeks after a booster TT vaccine

- 23-valent pneumococcal polysaccharide vaccine (23-PPV) response and 13-PCV booster response:

The proportion of patients in Groups A1, A2, A (A1 and A2 combined), and B with positive responses against an individual anti-pneumococcal antibody serotype measured 4 weeks after the 23-PPV (23 serotypes) (defined fully in Section [4.4.2.2](#))

The proportion of patients in Groups A1, A2, A (A1 and A2 combined), and B with a positive response against at least 2 out of the 23 serotypes measured 4 weeks after and 8 weeks after administration of the 23-PPV vaccine (defined fully in Section [4.4.2.2](#))

The proportion of patients in Groups A1, A2, A (A1 and A2 combined), and B with positive responses against at least 50% of the serotypes (≥ 12 of 23) measured 4 weeks after administration of the 23-PPV vaccine (defined fully in Section [4.4.2.2](#))

The proportion of patients in Groups A1, A2, A (A1 and A2 combined), and B with positive responses against each of the 23 serotypes measured 8 weeks after patients received the 23-PPV vaccine (which is 4 weeks after Group A1 received the booster 13-PCV) (defined fully in Section [4.4.2.2](#))

Mean levels of anti-pneumococcal antibody (23 serotypes) in patients in Groups A1, A2, A (A1 and A2 combined), and B measured immediately prior to, 4 weeks after and 8 weeks after patients received the 23-PPV (this is 4 weeks after Group A1 received the 13-PCV immunization)

- KLH

Mean levels of anti-KLH antibody (IgG) in patients in Groups A (A1 and A2 combined) and B measured immediately prior to the first administration of KLH and 4 weeks after the last administration of KLH

Mean levels of anti-KLH antibodies (IgG and IgM) in Groups A (A1 and A2 combined) over time at 4, 8, and 12 weeks after first KLH immunization

- Influenza vaccine response:

Proportion of patients in Groups A2 and B who achieve seroprotection defined as specific hemagglutination inhibition (HI) titers >40 at 4 weeks post-immunization

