4.4.1 Primary Immunology Endpoint

The primary outcome measure is the proportion of patients in Groups A and B with a positive response (IgG) to TT adsorbed vaccine measured 8 weeks after TT booster vaccine administration. Positive response is defined as follows:

- For patients with pre-immunization tetanus antibody titers <0.1 IU/mL, a positive response to the booster TT immunization is defined as an antibody titer ≥ 0.2 IU/mL measured 8 weeks after immunization.
- For patients with pre-immunization tetanus antibody titers ≥ 0.1 IU/mL, a positive response to the booster TT immunization is defined as a 4-fold increase in antibody titers measured 8 weeks after immunization compared with pre-immunization levels.

The number and proportion of patients with a positive response to TT adsorbed vaccine will be presented by treatment group. The difference between treatment groups A and B in positive response rates and the associated 95% CI will also be presented using a normal approximation method.

Levels of anti-tetanus antibody in patients in Groups A and B measured 8 weeks after a booster TT vaccine administration will be summarized descriptively by treatment, showing the following summary statistics:

- Number and percentage of patients with values \leq LLQ
- Number and percentage of patients with values $>$ LLQ
- Geometric mean of known values $>$ LLQ
- 95% CI for geometric mean of known values $>$ LLQ, calculated using a normal approximation method on the log scale and then back-transformed to the original scale
- Geometric mean of all nonmissing values, imputing $LLQ \div 2$ for values \leq LLQ
- 95% CI for geometric mean of all nonmissing values, imputing $LLQ \div 2$ for values \leq LLQ, calculated using a normal approximation method on the log scale and then back-transformed to the original scale
- Median of known values $>$ LLQ
- Median of all nonmissing values, imputing $LLQ \div 2$ for values \leq LLQ

To aid comparison back to pre-vaccination levels, the following pre-vaccination summary statistics will also be included in the tabular summary at 8 weeks:

- Geometric mean of known pre-vaccination values $>$ LLQ
- Geometric mean of all nonmissing pre-vaccination values, imputing $LLQ \div 2$ for values \leq LLQ

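### The influenza GMT ratio is summarized by an unqualified mean and SD with no CI or A2 versus B estimate, and KLH has no planned Group A versus Group B estimate

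*SAP*

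**What the plan says.** **Influenza.** SAP 4.4.2.4 lists a strain-specific post:pre-vaccination GMT ratio and states that for this endpoint "Groups A2 and B will be summarized descriptively by treatment group; summary statistics calculated will include mean, median, SD, minimum, and maximum". The mean is not called geometric. No CI and no A2 versus B contrast are given for this line. The line just before it, on the GMTs at 4 weeks, uses the level statistics of SAP 4.4.1: geometric means whose CIs are "calculated using a normal approximation method on the log scale and then back-transformed to the original scale". Protocol 6.4.1 states: "The mean level of antibody parameters will be presented using geometric means".

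**KLH.** Protocol 2.2 sets secondary objective 3: "To characterize the humoral immune response (IgG and IgM) to KLH in Group A patients compared with Group B patients". SAP 4.4.2.3 summarizes IgG and IgM at 4, 8 and 12 weeks after the first KLH dose, by treatment group, with the same 4.4.1 statistics. It specifies no A/B ratio or difference.

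**The KLH outcome listing.** Protocol 3.4.2 has "Mean levels of anti KLH antibodies (IgG and IgM) in patients in Groups A (A1 and A2) and B measured over time". SAP 2.2.2 has "Mean levels of anti-KLH antibodies (IgG and IgM) in Groups A (A1 and A2 combined) over time", without Group B. SAP 2.2.2 also limits the pre-first-dose to post-last-dose measure to IgG, where the protocol has IgG and IgM.

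**The concern.** Elsewhere, where the SAP wants a geometric mean, it says so and attaches a log-scale CI. The GMT-ratio line does neither and lists an SD, minimum and maximum. These exist for a set of per-patient ratios, but not for a single ratio of group GMTs. Followed literally, the report would carry an arithmetic mean fold-rise under the name of a GMT ratio. It would disagree with the GMTs beside it and give no measure of precision for the group comparison.

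For KLH, the stated comparison has no planned estimate. Objectives 1 and 2 (pneumococcal) and 4 (influenza) receive between-group differences with 95% CIs in SAP 4.4.2.2 and 4.4.2.4. Objective 5 (MRI) is not a between-group objective. KLH has no responder endpoint that could supply a contrast. Absence of hypothesis testing (SAP 4.4) does not explain the gap, because the SAP plans between-group CIs for the other antigens without testing. A versus B is also the randomized contrast, free of the caution that the SAP attaches to A1 and A2. Protocol 5.1.1.6 already draws the comparative conclusion that the KLH response was lower with ocrelizumab, so the size of that reduction needs a defined estimate.

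**Working it through.** The plan gives no figure of its own on this point, so there is none to reproduce.

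**Inputs.** About 100 patients at 2:1 and about 33 in A2 (protocol 3.1 and 6.1), taken here as A = 66, A2 = 33 and B = 34. The documents give no SD of log titer. A log-normal model with natural-log SD s from 0.8 to 1.5 is an assumption.

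**1. Arithmetic against geometric mean fold-rise.** Under the model the ratio is exp(s²/2).

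| s | exp(s²/2) |
|---|---|
| 0.8 | exp(0.32) = 1.38 |
| 1.2 | exp(0.72) = 2.05 |
| 1.5 | exp(1.125) = 3.08 |

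**2. The A2/B contrast with equal spread.** Simulation of 40,000 trials, 33 versus 34 patients, geometric mean fold-rise 3 in both groups, so the true ratio is 1. Both contrasts have median 1.00. Ranges are 2.5 to 97.5 percentiles.

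| s | Ratio of arithmetic means | Ratio of geometric means | Ratio of log-scale sampling SDs |
|---|---|---|---|
| 0.8 | 0.64 to 1.57 | 0.68 to 1.47 | 1.17 |
| 1.2 | 0.45 to 2.20 | 0.56 to 1.78 | 1.37 |
| 1.5 | 0.32 to 3.09 | 0.49 to 2.05 | 1.57 |

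The arithmetic contrast is unbiased here, but less precise.

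**3. The contrast with unequal spread.** Same set-up, true ratio 1, wider-spread group over narrower. The ratio of geometric means has median 1.00 in every row.

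| s in the two groups | Median ratio of arithmetic means (2.5 to 97.5%) |
|---|---|
| 1.2 and 1.0 | 1.22 (0.62 to 2.52) |
| 1.2 and 0.8 | 1.43 (0.78 to 2.80) |
| 1.5 and 0.8 (extreme) | 2.03 (0.95 to 5.20) |

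**4. KLH A/B ratio of geometric means, 66 versus 34.** The 95% CI is the estimate divided and multiplied by exp(t × s × √(1/66 + 1/34)), with 98 df, t = 1.984 and the root equal to 0.2111. This gives 1.40, 1.65 and 1.87 at s = 0.8, 1.2 and 1.5.

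**5. What side-by-side group CIs give instead, at s = 1.2.** The log half-widths are 1.96 × 1.2/√66 = 0.2895 and 1.96 × 1.2/√34 = 0.4034.

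- Non-overlap needs a log difference of 0.2895 + 0.4034 = 0.6929, a ratio of 2.00.
- A direct CI excludes 1 at √(0.2895² + 0.4034²) = 0.4965, a ratio of 1.64.
- The overlap rule is stricter by 0.6929/0.4965 = 1.40 on the log scale. With a common s this factor does not depend on s.

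**The case against.** The strongest reply concerns weight.

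- **KLH is recoverable.** The groups are independent and SAP 4.4.2.3 gives geometric means with log-scale CIs for both. The root-sum-of-squares in step 5 recovers the direct CI, and the 1.40 penalty falls only on a reader who judges by overlap. This is correct, but it leaves the comparison named in the objective for the reader to construct.
- **Levels are treated alike for all antigens.** Tetanus, pneumococcal and influenza levels have no between-group ratio either, and protocol 6.4.1 promises none. True, but those antigens have responder-rate differences with CIs, and KLH has nothing comparable.
- **Influenza is otherwise well covered.** SAP 4.4.2.4 gives A2 minus B differences with 95% CIs for seroprotection, 2-fold rise, 4-fold rise and seroconversion. A median ratio is planned, and GMT(post)/GMT(pre) follows by division. The gap is confined to the GMT-ratio line; division gives no paired CI.
- **The mean may be meant as geometric.** The endpoint's name and protocol 6.4.1 point that way. If so, steps 1 to 3 do not apply, but the scale is still undefined in the SAP, and the CI and A2/B ratio are still missing.
- **The listing mismatch is editorial.** SAP 4.4.2.3 already has both groups and both isotypes, and 12 weeks after the first KLH dose is 4 weeks after the last. This stands.
- **Values at or below LLQ.** KLH is a new antigen given during B-cell depletion, so many low values are plausible. An A/B ratio using LLQ/2 could then depend on the LLQ, and the precision in step 4 may not hold. This is a fair limit on the fix.

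**Conclusion.** The concern holds and should be corrected, with moderate impact. As written, the GMT-ratio statistic does not match its name, and secondary objective 3 has no planned between-group estimate. The endpoints are secondary and descriptive, and the primary endpoint is untouched.

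Under the assumed log-normal model with s from 0.8 to 1.5, a literal reading inflates the reported mean fold-rise by 1.38 to 3.08 relative to the geometric mean. The group contrast is distorted only if spread differs between A2 and B (median 1.43 instead of 1 at s = 1.2 and 0.8). With equal spread it only loses precision. For KLH, what is missing is a ratio that could be stated to within a factor of about 1.40 to 1.87. These sizes rest on the assumed SDs and on full group sizes; the SAP's Observed Cases Population may be smaller.

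**What to change.** - **SAP 4.4.2.4.** Replace the GMT-ratio statistics with, per group and strain, the geometric mean of patient post:pre ratios (LLQ/2 for values at or below LLQ) with a 95% CI computed on the log scale and back-transformed. Add the A2/B ratio of these with a 95% CI. Keep the existing caution about non-random assignment to A2.
- **SAP 4.4.2.3.** Add the unadjusted A/B ratio of geometric means (all non-missing values, LLQ/2 rule) with a 95% CI for KLH IgG and IgM at 4, 8 and 12 weeks after the first dose. Show it beside the percentages at or below LLQ that are already planned, so that dependence on the LLQ is visible.
- **SAP 2.2.2.** Add Group B to the KLH over-time measure and IgM to the pre-first/post-last measure, to agree with protocol 3.4.2 and SAP 4.4.2.3.

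Protocol 1.1.4 and 5.1.1.6 show that Immunization Study Period results already exist. Estimates added now should be labelled as added after the original plan.

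The cost is SAP wording and two sets of programmed estimates: the fold-rise summaries with one A2/B ratio per influenza strain, and six KLH ratios (two isotypes at three timepoints). No new data and no hypothesis test are needed.
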